9.5 Study Size

Sample size calculation is based on the second part of the primary objective, especially on predicting exacerbations of a severe or moderate type as outcome.

Assuming a desirable sensitivity and specificity of 0.85 for our algorithm and requiring that the lower 95% confidence limit should be at least 0.50 (with a probability of 0.95) for this exploratory approach, the number of observed exacerbation events needed is 18 ([Flahault 2005](#)).

Assuming that patients with COPD within our eligibility criteria (GOLD stage II-IV with a history of at least 2 moderate and/or severe exacerbations within any 12 month period within the last 3 years and at least 1 moderate or severe exacerbation within the last 12 months) show a frequency of 2 moderate or severe exacerbations per year, participants with COPD will have 0.5 events in 3 months (the in-study time). Further assuming that event occurrence over 3 months for every individual participant follows a Poisson distribution with parameter $\lambda = 0.5$, the number of events in the overall study population is also Poisson distributed and the corresponding parameter is the sum of individual parameters λ . Calculations show that a λ of 30 is needed to reach an upper cumulative distribution probability of 0.99 for observing at least 18 exacerbations. Therefore, 60 participants are needed to observe at least 18 exacerbation events within the 3-month observation period.

The events of interest in the context of the present study are COPD exacerbations (severe or moderate), exactly the onset of an exacerbation. For building the binary classifier predictive models we also require “no exacerbation” events. We will sample such events randomly from periods with no exacerbations, avoiding 2 weeks before and after an exacerbation.

Considering a drop-out rate of 10%, the estimated number is 67 participants with COPD that need to be included in this study.

This recruitment number is also in good agreement with published studies with regards to the ability to build predictive models for exacerbations. Studies with similar recruitment numbers ([Yañez 2012](#)) have been able to predict exacerbations based on single parameters studied. Strong features can compensate for low numbers in COPD machine learning model building as shown in

[Al Rajeh 2020](#), and using several features improves the accuracy of predictive models as seen in [Jensen 2012](#).

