### 1.3.2 Study size

Sample size calculation is based on the second part of the primary objective, especially on predicting exacerbations of a severe or moderate type as outcome.

Assuming a desirable sensitivity and specificity of 0.85 for our algorithm and requiring that the lower 95% confidence limit should be at least 0.50 (with a probability of 0.95) for this exploratory approach, the number of observed exacerbation events needed is 18 (1).

Assuming that COPD patients within our eligibility criteria (GOLD stage II-IV with a history of at least 2 moderate to severe exacerbations within any 12 month period within the last 3 years and at least 1 exacerbation within the last 12 months) show a frequency of 2 moderate or severe exacerbations per year, COPD participants will have 0.5 events in 3 months (the in-study time). Further assuming that event occurrence over 3 months for every individual participant follows a Poisson distribution with parameter  $\lambda = 0.5$ , the number of events in the overall study population is also Poisson distributed and the corresponding parameter is the sum of individual parameters  $\lambda$ . Calculations show that a  $\lambda$  of 30 is needed to reach an upper cumulative distribution probability of 0.99 for observing at least 18 exacerbations. Therefore, 60 participants are needed to observe at least 18 exacerbation events within the 3-month observation period.

The events of interest in the context of the present study are COPD exacerbations (severe or moderate), exactly the onset of an exacerbation. For building the binary classifier predictive models we also require “no exacerbation” events. We will sample such events randomly from periods with no exacerbations, avoiding 2 weeks before and after an exacerbation.

Considering a drop-out rate of 10%, the estimated number is 67 COPD participants that need to be included in this study.

This recruitment number is also in good agreement with published studies with regards to the ability to build predictive models for exacerbations. Studies with similar recruitment numbers (2) have been able to predict exacerbations based on single parameters studied. Strong features can compensate for low numbers in COPD machine learning model building as shown in (3), and using several features improves the accuracy of predictive models as seen in Jensen 2012.

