Different machine learning algorithms will be evaluated, and their performance will be assessed by estimating their accuracy, specificity, sensitivity, and area under ROC metrics. Other usual evaluation metrics such as precision, positive predictive value (PPV), negative predictive value (NPV), F1-score will be computed.

This analysis will be performed on the COPD cohort. Internal cross-validation will be tested.

The following models will be used:

- Logistic regression
- Random Forest
- K-nearest neighbors
- Boosting methods (e.g., Gradient boosting machine, GBM)
- Support vector machines (SVM)

Other methods may be tested.

The development of those models will be based on the machine learning algorithms implementation of scikit-learn (12), a python package designed for predictive data analysis. Other packages may be considered if needed (e.g., H2O (13)).

To optimize the performance of the models, feature extraction and selection algorithms will be used.

Explanatory models will be built on top of the selected machine learning algorithm (14), as a way to support rationalization for physicians and regulatory organizations. Depending on the selected ML model selected, either model specific (for logistic regression, decision trees, k-nearest neighbors) or model agnostic methods will be considered (global methods as PDP, ALE, functional decomposition, and local methods as LIME and Shapley values).

### 3.4.5.3 Secondary Objective 3

Objective 3 will be analyzed on the COPD cohort. For each pair of variables and outcomes ( $x, y$ ) defined below, Pearson's correlation coefficient will be computed together with a 95% asymptotic confidence interval based on Fisher's Z transform.

In case of low variability in parameter values (e.g., exacerbation count), parameters may be treated as ordinal and analyzed in terms of Kendall's Tau statistic with non-parametric confidence interval (see (15)).

The following variable groups and outcomes will be paired and assessed at the indicated time points:

Group x	Group y	Time points for assessment
Sensor data (see section 2.1.4), daily averages (17 variables): physical activity, heart rate, resting heart rate, heart rate variability, temperature, respiration rate, ratio of in- vs expiration time, cough frequency, sleep pattern (hours of sleep)	CAT summary score: Self-assessed patient's health status by CAT questionnaire.	Baseline (Day 0), End of study visit

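### The study is sized on a lower 95% confidence limit for sensitivity and specificity, but the visible analysis text for the prediction model plans point estimates only

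*SAP*

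**What the plan says.** The sample size is tied to Primary Objective 2, the model for moderate or severe exacerbations. SAP 1.3.2 sets out its premise as "Assuming a desirable sensitivity and specificity of 0.85 for our algorithm" and continues "requiring that the lower 95% confidence limit should be at least 0.50 (with a probability of 0.95) for this exploratory approach", from which "the number of observed exacerbation events needed is 18". Protocol 9.5 has the same text. Neither document says whether the limit is one-sided or two-sided, or by which method it is calculated.

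The analysis of that objective is in SAP 3.4.5.2 and Protocol 9.7.2.1. In both, several algorithms are compared and "their performance will be assessed by estimating their accuracy, specificity, sensitivity, and area under ROC metrics". The SAP adds precision, PPV, NPV and F1, and mentions internal cross-validation without giving a scheme. No confidence interval is attached to any of these metrics. The general specifications (SAP 3.4.1) and the sensitivity analyses (SAP 3.4.6) do not supply one.

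Elsewhere the SAP does plan intervals: t-based 95% intervals for the daily mean plots under Objective 1, and 95% intervals for the correlations under Objective 3 (Fisher's Z, or a non-parametric interval for Kendall's tau).

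**The concern.** The one quantity on which the size of the study rests, a lower confidence limit, is not among the planned outputs for the objective that it was meant to serve. Followed as written, the report could give a sensitivity such as 0.83 with no indication of how imprecise a figure from 18 to 30 events is. Protocol Sections 7 and 9.9 say that the models must be validated in later studies, and whoever plans those studies will need that uncertainty.

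If an interval is added only after the data are seen, its method and sidedness would be chosen at that point, and for some results the choice decides on which side of 0.50 the limit falls.

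**Working it through.** **Inputs from the documents** (Protocol 9.5, SAP 1.3.2): true value 0.85; lower 95% limit at least 0.50 with probability 0.95; 18 events; 2 events per participant-year, so 0.5 in 3 months; Poisson mean 30; drop-out 10%.

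**Reproducing the plan's figures**

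- For n events, find the smallest number detected, r, whose lower 95% limit is at least 0.50; then find the smallest n with P(X ≥ r | n, 0.85) ≥ 0.95.
- One-sided exact (Clopper-Pearson) limit: n = 17 gives 0.901; n = 18 has r = 13 and P(X ≥ 13) = 0.958. So 18 reproduces.
- Other readings: two-sided exact needs 23, one-sided Wilson 17, two-sided Wilson 21, one-sided Wald 14. Two-sided Wald also gives 18, with the same threshold of 13. Among exact limits, only the one-sided version gives 18.
- Poisson: P(X ≥ 18 | mean 30) = 0.993. Then 30/0.5 = 60, and 60/0.9 = 66.7, rounded up to 67.

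The sizing is sound; the gap is on the analysis side.

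**What a point estimate leaves open** (exact limits for sensitivity)

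| Detected | Estimate | One-sided 95% lower limit | Two-sided 95% interval |
|---|---|---|---|
| 12/18 | 0.667 | 0.446 | 0.410 to 0.867 |
| 13/18 | 0.722 | 0.502 | 0.465 to 0.903 |
| 14/18 | 0.778 | 0.561 | 0.524 to 0.936 |
| 15/18 | 0.833 | 0.623 | 0.586 to 0.964 |
| 25/30 | 0.833 | 0.681 | 0.653 to 0.944 |

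At 13/18 the limit is above 0.50 one-sided and below it two-sided. At a true 0.85 with 18 events, the probability that the limit reaches 0.50 is 0.958 one-sided and 0.879 two-sided. Eighteen is the minimum and 30 the expected count. At 30 events the one-sided limit reaches 0.50 from 20/30 (0.501), with probability 0.997 at a true 0.85.

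**Why a plain binomial limit is not enough for sensitivity**

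Participants can contribute more than one event. Under the plan's Poisson model with mean 0.5, the share of events from participants with two or more is 1 − P(X = 1)/0.5 = 1 − e^(−0.5) = 0.39. The model is also chosen from at least five algorithm families, and a binomial limit treats it as fixed in advance.

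**Specificity, under assumptions**

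The 18 events inform sensitivity only. Precision for specificity depends on how many exacerbation-free days are sampled, and the documents give neither that number nor an intraclass correlation (ICC). Assume 60 participants, true specificity 0.85, m days each and beta-binomial clustering. The design effect is 1 + (m − 1) × ICC: 1.4 for m = 5 and ICC 0.1, and 2.8 for m = 10 and ICC 0.2. Simulated coverage of a naive 95% exact interval is:

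- m = 5: 91% (ICC 0.1), 87% (ICC 0.2)
- m = 10: 86% (ICC 0.1), 77% (ICC 0.2)
- m = 2: 94% to 95%
- m = 1: about 97%, with no clustering to consider

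In the 5- and 10-day scenarios the naive lower limit stayed above 0.64 in every simulated study, so this under-coverage does not affect the comparison with 0.50.

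**The case against.** The strongest reply is that 0.50 is a planning input. Both documents attach it to an exploratory approach, and neither announces a verdict against it. This stands. A reader might infer that the study has a success criterion that goes untested. The protocol abstract, which describes the size as that required to show a sensitivity of at least 0.85, encourages that reading, but the calculation in Section 9.5 uses 0.85 as an assumed true value and 0.50 as a precision bound. The reply does not remove the gap, because a precision requirement is a statement about an interval and none is planned.

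A reader might also infer that the limit will never be examined. The documents do not support that either. SAP 3.4 sends table layouts to the TLF plan in Appendix 1, whose content is not in the text available here, and parts of SAP 3.4.5 are redacted. The point is therefore confined to the visible text, although the methods section is where interval method and sidedness belong.

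Two further objections stand in part. Figures at 18 events are close to the worst case under the plan, which is why those for 30 are shown beside them. The specificity coverage figures rest on assumed control days and ICC; with one or two days per participant the problem largely disappears.

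**Conclusion.** The point holds as a mismatch between sizing and analysis in the visible text. The sample size depends on a lower 95% limit, and the analysis of the same objective names only point estimates, so the report would not show whether the planned precision was reached. The missing information is substantial: an estimate of 0.83 has a 95% interval about 0.38 wide at 18 events (0.964 − 0.586) and about 0.29 wide at 30 (0.944 − 0.653). These widths assume independent events and a fixed model.

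The numbers 18, 60 and 67 are not in question. That the intended limit was one-sided and exact is an inference from its reproducing 18, since the documents do not say so. The specificity under-coverage of 91% down to 77% is conditional on 5 to 10 control days per participant and an ICC of 0.1 to 0.2. It is a reason to choose a participant-level method, not evidence that the 0.50 bound would be misjudged. In an exploratory study this should be corrected, but it does not undermine the design.

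**What to change.** Add to SAP 3.4.5.2, before the single final analysis:

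- Report 95% intervals for sensitivity, specificity and AUC from held-out predictions. Keep each participant whole across folds, and carry out model and feature selection inside the resampling loop.
- Use a bootstrap that resamples participants for every metric, so that repeat events and repeated control days are both covered.
- Beside it, give the one-sided 95% exact lower limit for sensitivity, as the exact version that reproduces 18 events, noting that it assumes independent events and a fixed model.
- Show the lower limits for sensitivity and specificity next to the 0.50 planning value, and state that this describes achieved precision and is not a success test.
- If the TLF plan already contains such intervals, refer to it and state method and sidedness in the text.

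The cost is SAP wording and some extra computing. No data, visits or participants are added, and 67 stands. The downside is that wide intervals will appear in the report.

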9.7.2.1 Primary Objectives

Primary objective 1): To describe the distribution of sensor collected data on physical activity, heart rate, heart rate variability, temperature, respiration rate, cough frequency, and sleep pattern, by severity of COPD exacerbations.

This analysis will be performed on the COPD participants set.

- Sensor collected data on physical activity, heart rate, heart rate variability, temperature, respiration rate, cough frequency, sleep pattern, at baseline (Day 0), in the period Day 8 to Day 14, and shortly prior (14 days prior to, 7 days prior) to, during an exacerbation and after an exacerbation (8 to 14 days after, 2 weeks after, 3 weeks after, up to 4 weeks after an exacerbation) will be reported as mean (SD) and/or median (Interquartile Range) for continuous variables and counts and frequency (%) for categorical variables. The analysis will be done on the group of severe or moderate exacerbations and on exacerbations by type.

Primary objective 2): To predict moderate or severe COPD exacerbations by building a statistical model employing sensor-derived data and demographic and medical covariates.

This objective aims at predicting the occurrence of a severe or moderate exacerbation, in other words, predicting an event out of the combined group of severe and moderate exacerbations. It is desirable to predict an AECOPD as early as possible, therefore dependency of model metrics on the time period before exacerbation will be explored.

As input to the model a number of algorithms (e.g. self-learning algorithms) for obtaining derived parameters such as cough frequency, physical activities and sleep pattern, heart rate variability, temperature, respiration pattern, cough frequency, or sleep pattern will be developed first using the labeling of activities dataset obtained via the app. Said derived features will help to understand the importance of different raw data patterns, so that explanatory models can be built on top of the machine learning algorithms (Molnar 2022), as a way to support rationalization for physicians and regulatory organizations.

Different machine learning algorithms (e.g. gradient boosting, SVMs, K-nn) will be evaluated, and their performance will be assessed by estimating their accuracy, specificity, sensitivity, and area under ROC metrics.

This analysis will be performed on the COPD participants set.

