- If the overlapping exacerbations have different types, the start date will be the start date of the first moderate or severe exacerbation, and the end date is the end date of the last moderate or severe exacerbation.

The following exacerbation-related outcomes are required for the analysis of primary objectives:

1. Time points (start and end dates) of mild/moderate/severe exacerbations for descriptive analysis of sensor variables (see Section 2.1.4)
2. Occurrence of moderate/severe exacerbations as binary outcome measured at the onset date of an exacerbation for predictive analysis. An event is the occurrence of a moderate/severe exacerbation. Non-exacerbation events (for definition see Section 1.3.2) will be sampled randomly from time points (days) outside of exacerbation periods (defined by start and end dates of each exacerbation) and avoiding 2 weeks before the onset time (day) and two weeks after the end time (day) of an exacerbation.

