### 3.4.4 Handling of missing data

For variables obtained only at the baseline visit, missing values will not be replaced.

For the self-reported satisfaction questionnaire items, collected at the end of study visit, missing values will not be replaced. For variables measured daily during the observation period such as sensor-generated data, CAT score, and labelling information, missing data will not be imputed for all descriptive statistical analyses performed. The CAT score and derived sensor variables may be imputed for the purpose of building machine learning models if needed to avoid loss of instances using a suitable imputation method (e.g., LOCF, Forward filling, multiple imputation [MI], recursive imputation, median imputation). Sensitivity analyses will be conducted to assess the impact of imputation.

For variables with values collected at baseline, at the exacerbation visit and at end of study visit, missing values will not be imputed for all descriptive statistical analyses. Lung function parameters and lab values may be imputed for the purpose of building machine learning models if needed to avoid loss of instances by LOCF method if the last (previous) available value is recorded within 2 weeks before the date of the visit of interest. In cases where no value for a variable is available for a participant, imputation strategies across instances may be used (e.g., median imputation or iterative imputation methods). Sensitivity analyses will be conducted to assess the impact of imputation.

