### 3.4.5 Analysis of outcomes

#### 3.4.5.1 Primary Objective 1

Descriptive statistics will be reported in terms of mean (SD) or median (IQR) for continuous variables, as well as counts and frequency (%) for categorical variables of sensor collected data described in section 2.1.4, comprised of

- physical activity,
- heart rate,
- resting heart rate,
- heart rate variability (10 variables),
- temperature,
- respiration rate,
- ratio of in- vs. expiration time
- cough frequency,
- sleep pattern (hours of sleep),
- frequency of additional medication

measured for each patient

1. at baseline (Day 0),
2. in the period Day 8 to Day 14 (intra-individual period average),
3. from 14 days prior to an exacerbation onset, in a 7-day sliding time window, in a 3-days sliding time window, and a 1-day sliding time window,
4. at the onset of an exacerbation (first day of exacerbation period),
5. from the end of an exacerbation to 14 days after, in a 7-day sliding time window, in a 3-days sliding time window, and a 1-day sliding time window,
6. 14, 21, and 28 days after an exacerbation.

The analysis will be repeated for different exacerbation severities:

1. Exacerbations of any (moderate or severe) severity are counted
2. Only severe exacerbations are counted
3. Only moderate exacerbations are counted
4. Only mild exacerbations are counted

Results will be reported in one table per parameter, with descriptive statistics indexing rows and measurement times indexing columns.

For each continuous parameter, mean values will be plotted across all daily measurement time points during the 3-month observation period, together with 95% CIs based on the normal approximation (t-statistic).

### 3.4.5.2 Primary Objective 2

To predict moderate or severe COPD exacerbations by building a statistical model employing sensor-derived data and demographic and medical covariates.

To generate several features needed as input to the model a number of algorithms (e.g., self-learning algorithms) for obtaining derived parameters such as cough frequency, physical activities and sleep pattern will be developed first using the label dataset obtained via the app (see Section 3.4.3).

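### If scored on the sampled days, PPV, NPV and F1 for the exacerbation classifier will reflect an unstated sampling ratio and not the daily event rate

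*SAP*

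**What the plan says.** **Positive instances.** SAP 2.3.1 defines the outcome as "Occurrence of moderate/severe exacerbations as binary outcome measured at the onset date of an exacerbation for predictive analysis", so each event supplies one positive day.

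**Negative instances.** Protocol 9.5 says of the non-event days: "We will sample such events randomly from periods with no exacerbations, avoiding 2 weeks before and after an exacerbation". SAP 1.3.2 repeats this, and SAP 2.3.1 makes it specific to days, "avoiding 2 weeks before the onset time (day) and two weeks after the end time (day) of an exacerbation". Protocol 9.5 and SAP 1.3.2 both introduce the sampling with the words "For building the binary classifier predictive models we also require". No section says how many non-event days are drawn per event, per participant or in total.

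**Metrics.** Protocol 9.7.2.1 and SAP 3.4.5.2 list accuracy, specificity, sensitivity and area under the ROC curve. SAP 3.4.5.2 goes further: "Other usual evaluation metrics such as precision, positive predictive value (PPV), negative predictive value (NPV), F1-score will be computed". It places the analysis on the COPD cohort and mentions internal cross-validation. It does not say on which days the metrics are scored.

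**Lead time.** Protocol 9.7.2.1 states that "dependency of model metrics on the time period before exacerbation will be explored". SAP 3.4.5.2 does not carry this over. Sliding windows appear only in the descriptive analysis of SAP 3.4.5.1, for example "from 14 days prior to an exacerbation onset, in a 7-day sliding time window".

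**The concern.** PPV, NPV and F1 depend on the share of positives among the scored days as well as on sensitivity and specificity. Where the analyst sets that share by an unstated draw, the three metrics estimate no defined quantity: two analysts following this SAP with the same model could report very different values. Cross-validation within the sampled days does not help, because every fold keeps the sampled ratio. Stating the ratio would make the figures interpretable but would not turn them into daily figures.

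The models are intended as a basis for a future remote-monitoring solution. There, PPV tells a physician how often an alert is followed by an exacerbation. A PPV from a near-balanced sample would look far better than the same model would deliver day by day, and NPV would look worse.

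**Working it through.** **Inputs from Protocol 9.5 and SAP 1.3.2:** sensitivity (Se) and specificity (Sp) 0.85; 60 participants; 0.5 moderate or severe events each in 3 months, so 30 events.

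**Assumed, because the documents give no figure:** 91 days of follow-up; 10 exacerbation days per event (range 5 to 14); the sampling ratios; 0.85 holding on every scored day.

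**The plan's own figures reproduce.** With an exact binomial lower limit (5% lower tail), 18 is the smallest number of events for which the limit is at least 0.50 with probability 0.95 (0.958). For a Poisson mean of 30, the probability of at least 18 events is 0.993. 60/0.9 = 66.7, rounded up to 67.

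**Formulas**, with P positive and N negative days: TP = Se·P; FN = P − TP; TN = Sp·N; FP = N − TN; PPV = TP/(TP+FP); NPV = TN/(TN+FN); F1 = 2TP/(2TP+FP+FN).

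**Day counts**, P = 30 onset days throughout, so TP = 25.5 and FN = 4.5:
- All participant-days: 60 × 91 = 5460, so N = 5430.
- All days eligible under the plan's buffers: N = 5460 − 30 × (14 + 10 + 14) = 4320.

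| Days scored | N | PPV | NPV | F1 |
|---|---|---|---|---|
| Sample 1:1 | 30 | 25.5/30 = 0.85 | 0.85 | 0.85 |
| Sample 1:5 | 150 | 25.5/48 = 0.53 | 0.966 | 0.65 |
| Sample 1:10 | 300 | 25.5/70.5 = 0.36 | 0.983 | 0.51 |
| Sample 1:20 | 600 | 25.5/115.5 = 0.22 | 0.991 | 0.35 |
| All plan-eligible days | 4320 | 25.5/673.5 = 0.038 | 0.999 | 0.07 |
| All participant-days | 5430 | 25.5/840 = 0.030 | 0.999 | 0.06 |

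The last two rows are close, so the gap comes from the ratio and hardly at all from the buffers.

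**Weighting removes the dependence on the ratio.** At 1:10 the sampling fraction is 300/4320, so each non-event day has weight 14.4. The 45 false positives become 45 × 14.4 = 648, and PPV = 25.5/673.5 = 0.038, the value on all eligible days.

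**Sensitivity to the assumptions:**
- 5 or 14 exacerbation days per event (N = 4470 or 4200): PPV on eligible days 0.037 or 0.039.
- 77 or 105 days of follow-up, all participant-days (N = 4590 or 6270): 25.5/714 = 0.036 or 25.5/966 = 0.026.
- The planned minimum of 18 events, all participant-days: 15.3/(15.3 + 816.3) = 0.018.

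**Longer windows, if adopted.** Suppose every day in a pre-onset window counted as positive, which SAP 2.3.1 does not provide for. On all 5460 days:
- 7 days (P = 210, N = 5250): 178.5/966 = 0.185.
- 14 days (P = 420, N = 5040): 357/1113 = 0.32.

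Leaving out exacerbation days and any pre-onset buffer days outside the window (N = 4740) gives 178.5/889.5 = 0.20 and 357/1068 = 0.33. Simulating that second version, with windows cut at the limits of follow-up and overlaps resolved, gives 0.18 and 0.29.

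**Accuracy** stays at 0.85 for any ratio when Se = Sp. For assumed unequal values it moves:
- Se 0.70, Sp 0.90: 0.80 at 1:1; on all participant-days (21 + 4887)/5460 = 0.90.
- Se 0.90, Sp 0.70: 0.80 at 1:1; on all participant-days (27 + 3801)/5460 = 0.70.

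**The case against.** **The scoring set is inferred.** A reader might conclude that the plan commits to reporting an inflated PPV. It does not: the sampling is introduced as a step in building the models, no section says the metrics are scored on the sampled days, and the contents of the TLF plan are not visible. This stands, and the point is therefore conditional. Even so, SAP 2.3.1 describes the sampled set as serving the predictive analysis and no other set is defined, so the SAP should confirm or exclude this reading.

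**The direction is not fixed.** A reader might infer that PPV is always overstated. A 1:10 sample (0.36) is close to a 14-day window (0.29 to 0.33), and a 1:20 sample (0.22) falls below it. This stands too. A large gap needs a near-balanced sample or a short window, and the plan fixes neither. With the plan's own onset-day positive, however, every ratio tabulated gives a PPV well above 0.03 to 0.04.

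**The metrics are additional ones in an exploratory study.** They follow the four main metrics, Protocol 9.7.2.1 does not list them, and Protocol section 7 leaves validation to future studies. A reader can recompute PPV from sensitivity and specificity at any event rate, but only if aware that the reported value depends on the sampling. This limits the severity without removing the point.

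**Conclusion.** The point holds in conditional form and is minor to moderate. If the metrics are scored on the sampled days, PPV, NPV and F1, and accuracy when sensitivity and specificity differ, are set partly by an unstated ratio. At 0.85/0.85, PPV is 0.85, 0.36 or 0.22 at assumed ratios of 1:1, 1:10 or 1:20. For the plan's onset-day positive it is about 0.030 on all participant-days and 0.038 on all plan-eligible days. The daily figures rest on 30 events in 60 participants over an assumed 91 days. The 0.038 also assumes 10 exacerbation days per event, though 5 to 14 days changes it little.

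It would go too far to infer that the classifier assessment or the sample size is unsound. Sensitivity, specificity and AUC do not depend on the ratio, although on sampled days specificity and AUC describe only days outside the buffers. The 18 events and 67 participants do not rest on PPV, NPV or F1.

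**What to change.** In SAP 3.4.5.2:

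1. State the sampling ratio and the set of days on which each metric is scored.
2. Compute PPV (once, since precision is the same quantity), NPV, F1 and accuracy from held-out predictions. Score them either on all participant-days with usable sensor data, or on the sampled days with each non-event day weighted by the inverse of its sampling fraction. In the weighted version, say that the 2-week buffer days are excluded. Otherwise drop PPV, NPV and F1.
3. Keep the onset day as the positive, as in SAP 2.3.1. If a longer window is explored under Protocol 9.7.2.1, state which days count as positive and report the metrics for each window.
4. If in-exacerbation days are left out of scoring, leave out only those after onset, because the onset day is the first day of the exacerbation period and is the plan's own positive. Do not drop pre-onset days from any figure described as the real daily rate: dropping them requires knowing that an onset will follow.

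**Cost.** SAP wording and one extra scoring run on data already collected daily. Scoring all participant-days needs a usable-day rule that fits SAP 3.4.4, which allows that "The CAT score and derived sensor variables may be imputed for the purpose of building machine learning models if needed". The alert threshold also needs checking: for a probability model trained at 1:1 on onset days, the log-odds on all participant-days would be too high by about ln(5430/30) = ln 181 = 5.2. PPV and F1 will look less favourable if the sample would have been near balanced.
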